10 DAY EVALUATION

Following 10 days of study treatment administrations (20 treatment administrations) with the Erchonia® EVRL (approximately halfway through the treatment administration phase), the following will be recorded on the provided case report forms by the subject at home.

- Visual Analog Pain Scale (VAS) Degree of Foot Pain Rating

3 WEEK EVALUATION: STUDY ENDPOINT

Following completion of the entire 3 weeks of study treatment administrations with the Erchonia® EVRL, the following will be recorded on the provided case report forms by the subject at home as outlined in the STUDY TEST BATTERY section above. These recordings will form the study endpoint data set from which change from baseline will be evaluated with respect to assessing study outcome

- Visual Analog Pain Scale (VAS) Degree of Foot Pain Rating
- Neuropathic Pain Symptom Inventory (NPSI)
- Subject Satisfaction With Study Outcome
- Perceived Treatment Group

POST-TREATMENT ACTIVITIES

7 WEEK EVALUATION: 4 Weeks Post-Treatment

Four weeks following the completion of the 3-week treatment administration phase, the following will be recorded on the provided case report forms by the subject at home, as outlined in the STUDY TEST BATTERY section above.

- Visual Analog Pain Scale (VAS) Degree of Foot Pain Rating
- Neuropathic Pain Symptom Inventory (NPSI)
- Subject Satisfaction With Study Outcome
- Perceived Treatment Group

COMPLIANCE ASSESSMENT LOG

The subject will record each day when they have administered a treatment with the Erchonia® EVRL Laser.

CHANGE IN MEDICATION RECORD SHEET

If at any time during the treatment and/or post-treatment administration phases the subject has a change in his or her medication use (cessation of prior medication, change in dosage/frequency of use of a current medication, addition of a new medication) the subject will record the medication name, dose/frequency of use, expected duration of medication use, and the reason for the change in the Change in Medication Record Sheet.

ADVERSE EVENTS

It is unlikely and not expected that any adverse events will result from implementation of this clinical study protocol. Prior clinical trials using low level laser light have not typically yielded any adverse events or reactions. However, potential adverse events that may feasibly occur from application of the Erchonia® EVRL include, but are not necessarily limited to skin irritation, discoloring, rash, indentations, and infection.

PRIVACY AND CONFIDENTIALITY

Records for each subject in this clinical study will be maintained in separate files in a locked filing cabinet at the respective test site. The investigator at the test site will be responsible for ensuring that all records for a subject pertaining to his or her participation in the clinical study are maintained in the subject's file at all times other than when information is being recorded on them.

Copies of all subject case report forms will be made and supplied to the study statistician and Erchonia Corporation who will each maintain these copies in a separate clinical study file that is kept in a locked filing cabinet on their respective premises. The original records will be maintained at the respective test sites.

Subjects' identities will be kept confidential by assigning each subject a unique de-identified subject ID upon acceptance into the study. The subject ID will comprise the investigator's two initials (first and last name initials) and a three-digit number that will be based upon the subject's order of entry into the clinical study. For example, under Study Investigator John Black, the third subject enrolled in the study would have a subject ID of JB003.

MONITORING OF THE CLINICAL STUDY

A Clinical Trial Monitoring Plan will be in place to ensure on-going compliance and accuracy of procedures throughout the trial.

STATISTICAL ANALYSIS

STUDY ANALYSIS POPULATIONS

(i) Intent-to-Treat (ITT) Population

The Intent-to-Treat (ITT) analysis population is defined as all consented and enrolled subjects. The ITT population will comprise the principal population analysis for evaluation of study primary efficacy outcome.

(ii) Per Protocol Population

The per protocol analysis population is defined as all consented and enrolled subjects who completed the entire clinical study per protocol, inclusive of all treatment administrations and all study activities and assessments per protocol without missing data or major protocol deviations. The per protocol population will comprise the secondary population analysis of the study primary efficacy outcome to provide support for the principal ITT population analysis as well as for all secondary outcome assessments.

HANDLING OF MISSING DATA

Based on over twenty-five (25) years of experience conducting comparable clinical trials through the study Sponsor, Erchonia Corporation, the relatively small sample size, the short duration of the trial, and the minimal requirements and commitments required from enrolled subjects, it is anticipated that withdrawal and lost-to-follow-up rates will be minimal and so will be missing data. Therefore, the single imputation methodology is selected as that to be implemented to account for any missing data. Single imputation methodology is applicable to impute missing values when a dataset is small, the number of missing values is small, the missing data is assumed to be Missing Completely at Random (MCAR), and outcome analysis procedures are simple. The single imputation methodology selected for this study is whichever is more conservative of the mean or the median of the variable for the treatment group from which the missing data emanated.

BASELINE RECORDINGS

SAMPLE DEMOGRAPHICS

Sample demographics recorded at Baseline assessment will be summarized descriptively by treatment group, using mean, standard deviation, median and range (minimum, maximum) for the continuous variable of subject age in years, and by number (N) and percentage (%) for the categorical sample variables of gender and ethnicity. Sample demographics will be compared for differences between treatment groups and test sites. Any identified differences will be explored with respect to potential impact on study outcome.

NEUROPATHY VARIABLES

Sample neuropathy continuous variables recorded at Baseline assessment of months since diagnosis of diabetes, and months since onset of peripheral neuropathy foot pain will be summarized descriptively by treatment group, using mean, standard deviation, median and range (minimum, maximum). The categorical Baseline neuropathy variable of presence or absence of insulin dependency will be summarized descriptively by number (N) and percentage (%) per category. Sample demographics will be compared for differences between treatment groups and test sites. Any identified differences will be explored with respect to potential impact on study outcome.

MEDICATION AND TREATMENT

The below medication and treatment usage as recorded at Baseline assessment will be summarized categorically by, and compared between, treatment groups using number (N) and percentage (%):

- (i) Current medications taken for relief of diabetic foot pain
- (ii) Prior treatment approaches for relief of diabetic foot pain
- (iii) Concomitant medication and therapy use: non-pain relief indications

PRIMARY EFFICACY OUTCOME MEASURE: CHANGE IN SUBJECT SELF-REPORTED VAS PAIN RATING FROM BASELINE TO STUDY ENDPOINT

Primary efficacy outcome measure for this clinical study will be a statistically significant difference in the proportion of subjects between active and placebo treatment groups who achieve a clinically meaningful and statistically significant decrease in self-reported VAS pain rating from Baseline (pre-treatment) to study Endpoint (Week 3).

The principal primary efficacy outcome evaluation will be performed for the study intent-to-treat (ITT) population according to the following pre-determined primary efficacy success criteria.

Individual Subject Success Criteria

Individual subject success criteria is defined as a 30% or greater decrease ($\geq 30\%$) in self-reported pain rating on the 0 to 100 Visual Analog Scale (VAS) at study Endpoint (Week 3) relative to Baseline.

Overall Study Success Criteria.

Overall study success criteria defined as at least a 35% difference between treatment groups, comparing the proportion of individual successes in each group. It is anticipated that about 55% of subjects in the active treatment group will meet the individual success criteria and about 20% of subjects in the placebo treatment group will meet the individual success criteria.

The clinical relevance of a 30% change in VAS score has been well established by FDA's Division of Physical Medicine and Rehabilitation Devices. The following Erchonia Corporation light therapy devices (Product Code NHN) obtained FDA 510(k) clearance based on clinical trials employing the 30% VAS change as the primary efficacy endpoint for pain reduction:

1. K221987; 09/01/22: "Erchonia® GVL: is indicated while using the green and violet diode simultaneously, for adjunctive use in providing temporary relief of minor chronic neck and shoulder pain of musculoskeletal origin."
2. K191257; 08/08/19: "Erchonia® EVRL: is indicated while using the red and violet diode simultaneously, for adjunctive use in providing temporary relief of minor chronic neck and shoulder pain of musculoskeletal origin."
2. K180197; 5/21/18; "Erchonia® FX-635: is indicated for the following two indications:
 - a. as an adjunct to provide relief of minor chronic low back pain of musculoskeletal origin.
 - b. as an adjunct to reducing chronic heel pain arising from plantar fasciitis."
3. K132940; 04/14/14: "The Erchonia Allay laser is indicated as an adjunct to reducing chronic heel pain arising from plantar fasciitis."

4. K012580; 01/17/02: "The TUCO Erchonia PL2000 is indicated for adjunctive use in providing temporary relief of minor chronic neck and shoulder pain of musculoskeletal origin."

Evaluation Time Point

The study end evaluation time point at which primary study success will be analyzed is at three weeks post-baseline, following completion of the 42nd and final study treatment administration with the Erchonia® EVRL.

Hypotheses

The pre-established null and alternative hypotheses for the primary efficacy outcome evaluation were the following:

(i) *Null Hypothesis:* The difference in the proportion of individual subject successes between the active and placebo treatment groups will be less than 35%.

$$H_0: \mu_A - \mu_P < 35\%$$

Where 'A' = active treatment group; and 'P' = placebo treatment group

(ii) *Alternative Hypothesis:* The difference in the proportion of individual successes between the active and placebo treatment groups will be 35% or greater in favor of the active treatment group.

$$H_1: \mu_A - \mu_P \geq 35\%$$

Where 'A' = active treatment group; and 'P' = placebo treatment group

(i) Responder Rate Analysis

Principal determination of study primary outcome success as defined will be according to Responder Rate Analysis calculated by determining the percentage of individual subject successes in each of the active and placebo treatment groups, separately, and then subtracting the two proportions to attain the difference in proportions between the two treatment groups. Overall Study Success will be demonstrated if this difference is $\geq 35\%$ in favor of the higher proportion occurring for the active treatment group.

(ii) Chi-Squared Analysis of Proportions

A chi-squared analysis to assess the significance of the difference in the proportion of individual subject successes (Responder Rate) between the active and placebo treatment groups will be performed. A two-tailed significance level of 5% will be considered statistically significant.

(iii) ANCOVA of Mean Change in Diabetic Peripheral Neuropathy Foot Pain VAS Ratings

Parametric Analysis of Covariance (ANCOVA) with the mean change from Baseline to study Endpoint (Week 3) in diabetic peripheral neuropathy foot pain ratings on the 0-100 VAS as the dependent variable, treatment group as the independent variable of interest, and Baseline diabetic peripheral foot pain VAS rating as a covariate will be performed. A two-tailed significance level of 5% was predetermined to be considered statistically significant.

SECONDARY EFFICACY OUTCOMES

The following secondary efficacy outcomes will be evaluated to provide support for the primary efficacy outcome analysis. **As no claims are intended to be made based on the secondary efficacy outcome evaluations, secondary efficacy outcome analysis will be performed for the per protocol analysis population only and statistical analyses will not be performed; secondary efficacy outcomes data will be presented descriptively only.**

(i) Diabetic Peripheral Neuropathy Foot Pain VAS Ratings Across Study Progression

Descriptives of mean, standard deviation (SD), median, and range (minimum, maximum) will be presented in a table for the degree of pain ratings recorded on the 0-100 VAS for diabetic peripheral neuropathy pain at each of the four (4) study assessments of Baseline (pre-treatment), Day 10 (Post-Baseline), Endpoint (3 Weeks Post-Baseline), and Follow-Up (7 Weeks Post-Baseline - 4 Weeks Post-Treatment End) by treatment group.

(ii) Neuropathic Pain Symptom Inventory (NPSI) Scores Across Study Progression

Descriptives of the mean, standard deviation (SD), median and range (minimum, maximum) for each of the five (5) dimension scores on the NPSI and the Total NPSI score will be presented in a table for each of the three study assessments of Baseline, Endpoint (Week 3), and Follow-Up (Week 7) by treatment group.

SATISFACTION WITH STUDY OUTCOME RATINGS

Subject satisfaction scores will be presented descriptively in a table as number (N) and percentage (%) per response category (Very Satisfied, Somewhat Satisfied, Neither Satisfied nor Dissatisfied, Not Very Satisfied, Not at All Satisfied) at each assessment of Study Endpoint (Week 3) and Study Follow-Up (Week 7) by treatment group.

Ratings will be further categorized into 'positive satisfaction responses' by summing the 'very satisfied' and 'somewhat satisfied' categories. The proportion of 'positive satisfaction responses' in each category at each assessment visit between treatment groups will be compared using a chi-squared analysis with a two-tailed significance level of 5% considered statistically significant.

Additionally, Spearman's correlation analysis will be conducted to assess the relationship between subject satisfaction with treatment outcome ratings and mean change in subject VAS ratings for diabetic peripheral neuropathy foot pain from Baseline to study Endpoint (Week 3), and from Baseline to Follow-Up (Week 7) assessments.

CHANGES IN MEDICATION USE AND TREATMENT COMPLIANCE

Subject compliance with treatment administration and maintenance of medication use reported at baseline without change across study duration will be assessed and reported descriptively based on subject recordings on the Subject Daily Diary.

BLINDING EFFICACY EVALUATION

Blinding efficacy evaluation will be conducted through analysis of findings from the Subject Perceived Subject Group Allocation and Rationale responses, recorded at completion of the treatment administration phase (study endpoint).

Statistical evaluation of blinding efficacy will be performed as follows:

- (i) The number (N) and percentage (%) of subjects who correctly perceived their treatment group assignment and the percentage of subjects who did not correctly perceive their treatment group assignment will be calculated for each treatment group.
- (ii) A Chi-Squared Analysis to assess the significance of the difference in the proportion of subjects who accurately perceived their Baseline treatment group assignment between the active and placebo treatment groups at each of Endpoint (Week 3) and Follow-Up (Week 7) assessments will be performed. A two-tailed significance level of 5% will be considered statistically significant.

- (i) **Qualitative analysis confirmation:** Evaluation of the comments provided by the subject in the rationale section to explain the guess at group assignment will be evaluated and interpreted as follows to either support or negate the numerical findings:
 - *Positive blinding efficacy* will be supported through qualitative assessment of comments provided to support perceived group assignment that pertain to the determination being based on treatment efficacy or lack thereof, e.g.: 'My foot pain is much less than it used to be, so I believe I got the real treatment' or 'My foot pain hasn't really changed, so I believe I got the fake treatment.'
 - *Blinding will be determined to have failed* if comments provided to support perceived group assignment pertain to factors such as sensation/visual clues or overhearing conversations by research staff members.

INDIVIDUAL SUBJECT VAS RATINGS ACROSS STUDY DURATION

Individual subject data for the Primary Outcome Measure of diabetic peripheral neuropathy foot pain VAS Ratings as recorded at each of Baseline (pre-treatment) and Study Endpoint (Week 3) assessments, by Treatment Group, by Test Site, will be presented in table format.

INDIVIDUAL TEST SITE DATA

Key demographic and neuropathy variables and the primary outcome assessment for the ITT analysis population will be presented by treatment group by each of the four individual test sites participating in this study. Data will be presented in descriptive format only due to the small sample sizes that preclude statistical conclusions from being validly drawn.

SAFETY ANALYSES

Safety analyses will be based on all subjects who were randomized to the test or to the placebo treatment group. Safety will be assessed by evaluating and comparing frequency and incidence of observed and/or reported adverse events between test and placebo treatment groups. A chi-square test with a continuity correction will be performed to compare the percentage of subjects who had adverse events between test and placebo treatment group subjects.

INFORMED CONSENT

- Informed consent will be an agreement between the individual investigator and each subject, having the capacity to understand and make an informed decision. Consent will be obtained prior to each potential subject's participation in this clinical study.

- Each subject participating in this clinical study will be made aware of the fact that his or her participation involves research and the intent of the research, the expected duration of his or her participation and a description of the procedures that will be followed.
- Each subject will be made aware of the reasonably expected benefits he or she might receive, as well as any risks or potential discomfort that are involved.
- Each subject will also be made aware of alternative treatments available to him or her.
- Each subject will be made aware that his or her records will remain confidential, but that the FDA and the IRB has the right to inspect his or her records.
- Each subject will be told that his or her participation in the clinical study is voluntary, without force or influence from the investigator or sponsor.
- Each subject will be given the name and method of contacting the appropriate person(s) to answer his or her questions about the research and in the event of a research-related injury.

The informed consent form that will be used to collect the data from each subject in this clinical study can be found in **Appendix L**.

CASE REPORT FORMS

The case report forms that will be used to collect the data from each subject in this clinical trial can be found in **Appendix M**.

END OF DOCUMENT

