Subjects enrolled in the clinical study will not have been enrolled in the Human Factors Validation Testing study.

Each enrolled subject will be randomized to the active treatment group or to the placebo treatment group of the clinical study, as follows:

Active treatment group: Subjects randomized to the active treatment group will self-administer the study treatments with the active (true) Erchonia® EVRL laser in his or her own home.

Placebo treatment group: Subjects randomized to the placebo treatment group will self-administer the study procedures with a 'fake' (placebo) Erchonia® EVRL laser in his or her own home. The 'fake' (placebo) laser device will appear to the subject to be an active device but will not produce any therapeutic light output. The placebo laser device is designed to have the same physical appearance as the actual (active) laser device, including the appearance of any visible and invisible light output. Therefore, both the active and placebo devices emit light when activated that is indistinguishable to the subject. As the laser light does not put out any notable degree of heat or noise, these are also not distinguishing factors for subjects between the active and placebo devices.

Regardless of whether the subject self-administers the study treatments with the actual or the fake laser device, all subjects will be required to adhere to all phases of the entire protocol design.

DOUBLE BLIND DESIGN

This clinical study is a double-blind design, such that neither the subject nor the investigator is aware of whether the subject has been provided with the active or the placebo Erchonia® EVRL device. Unblinding will occur after the final data set has been fully analyzed.

The blinding procedure is as follows:

- 1) Each subject is randomly assigned to Treatment Group A or to Treatment Group B. Subjects assigned to Treatment Group A will receive the Erchonia® EVRL A and subjects assigned to Treatment Group B will receive the Erchonia® EVRL B. Only one individual employee at the study Sponsor site will know which label ('A' or 'B') corresponds to the actual (active) EVRL device and which label corresponds to the 'fake' device until the final study data set analysis is complete. That individual will ensure that this information is stored and maintained confidentially at the Sponsor's work site.

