- If using analgesics (pain medication), must be on a stable analgesic regimen (i.e., no changes to the prescribed analgesic regimen) over a period of at least 14 days prior to enrollment; and willing and able to not have planned upward dose titration of analgesics during the study period. The subject may elect to decrease analgesic use during the study. Cannabis prescribed for medicinal purposes would qualify as an analgesic in this context.
- Willing and able to refrain from engaging in any non-study procedure therapies for the management of foot pain throughout the course of study participation, including conventional therapies such as physical therapy, occupational therapy and hot or cold packs, as well as alternative therapies such as chiropractic care and acupuncture.
- Agrees to refrain from taking a dosage of analgesic (pain medication) for at least 6 hours before a scheduled VAS foot pain rating is to be recorded.
- Subjects' degree of foot pain on the 0-100 VAS, with "0" being no pain and "100" being worst pain imaginable, is 50 or greater.

EXCLUSION CRITERIA

A subject who satisfies any of the following criteria will be excluded from study participation:

- Pregnant or think they might be pregnant.
- Open wounds (sores, cuts, ulcers, etc.) around the feet
- Cancerous growths around the feet.
- Difficulty with hand dexterity sufficient to impact ability to administer treatments with the laser such as from severe arthritis in the hands, Multiple Sclerosis, Cerebral Palsy, Parkinson's Disease, Huntington's Disease, etc.

PRE-TREATMENT EVALUATION PHASE

The pre-treatment evaluation phase commences following successful study qualification.

BASELINE VARIABLES

- Baseline Foot Variables
- Medication and Treatment
- Insulin Dependency
- Subject Demographics

PRE-TREATMENT OUTCOME ASSESSMENTS

- Visual Analog Scale (VAS) Degree of Foot Pain Rating
- Neuropathic Pain Symptom Inventory (NPSI)

The Pre-Treatment Outcome assessments will serve as the Baseline data set.

AT-HOME TREATMENT ADMINISTRATION PHASE

A fully qualified enrolled subject will be provided either a Erchonia® EVRL A or B device based on his or her randomization to treatment group (see Randomization). Additionally, the enrolled subject will be provided the EVRL Proper Use Reference Guide (**Appendix D**) and applicable Case Report Forms (**Appendix M**) for capturing study outcome assessments.

TREATMENT ADMINISTRATION PROTOCOL

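### The plan does not say clearly whether a subject who stops the device early still gives the Week 3 VAS, and if it is missing the own-arm imputation rule may credit many active-arm stoppers, but few placebo stoppers, as successes.

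*Combined protocol and SAP*

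**What the plan says.** Timing of the rating:

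- The 3 Week Evaluation section sets the endpoint form "Following completion of the entire 3 weeks of study treatment administrations".
- Evaluation Time Point, in the statistical section, says the evaluation "is at three weeks post-baseline, following completion of the 42nd and final study treatment administration". It gives a calendar anchor and a dose anchor together.
- Secondary Efficacy Outcomes labels the endpoint as 3 weeks, and the follow-up as 7 weeks, post-baseline, with no dose condition.
- Subject Groups states that "all subjects will be required to adhere to all phases of the entire protocol design". It makes no mention of a subject who has to stop.

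Missing ratings:

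- The ITT "analysis population is defined as all consented and enrolled subjects", and it is the principal population for the primary outcome.
- Handling of Missing Data fills a gap with "whichever is more conservative of the mean or the median of the variable for the treatment group from which the missing data emanated", assuming data missing completely at random. It does not say whether the variable imputed is the Week 3 score, the change or the percent change.

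Reasons for stopping:

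- Exclusion Criteria bars subjects with "Open wounds (sores, cuts, ulcers, etc.) around the feet".
- Adverse Events says none are expected, but that possible ones "include, but are not necessarily limited to skin irritation, discoloring, rash, indentations, and infection".

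**The concern.** The calendar and dose anchors coincide only for a subject who gives all 42 sessions on schedule. Someone who stops at, say, session 20 has no 42nd session, and no sentence says whether the Week 3 form is still due.

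If that form is not completed, the imputation rule supplies a typical value from the subject's own arm. A stop for a foot wound or infection is plausibly related to the foot pain being rated, so missing completely at random is a poor description of it. Choosing the more conservative of mean and median helps only in part, because both candidates come from the same arm. If the arms perform as planned, the typical active value lies near or beyond a 30% reduction and the typical placebo value does not. The same safety stop can then count for the device in one arm and as a failure in the other.

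**Working it through.** **Inputs from the documents.** Success rates 55% and 20%; two-sided alpha 0.05; power 0.80; 29 evaluable and 32 enrolled per arm; individual success is a VAS decrease of at least 30%; baseline VAS at least 50; overall success is an observed difference of at least 35 points.

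**1. The plan's own sample size.** With pooled proportion (0.55 + 0.20)/2 = 0.375:

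n = [1.96 × √(2 × 0.375 × 0.625) + 0.8416 × √(0.55 × 0.45 + 0.20 × 0.80)]² / 0.35² = (1.342 + 0.537)² / 0.1225 = 28.8, so 29. Then 29 / 0.917 = 31.62, so 32. The figure reproduces.

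**2. Weight of one subject.** 1/32 = 3.1 points. Since 0.35 × 32 = 11.2, the active arm needs at least 12 more successes than placebo: 11/32 = 34.4 points misses and 12/32 = 37.5 meets.

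**3. How the rule scores a missing subject.** If the Week 3 VAS is imputed, the subject is a success when the imputed value is at most 0.7 × his or her own baseline. The documents give no SD or shape, so these are assumptions: 29 observed per arm; four baseline distributions on 50 to 100; percent change with SD 20 to 40 points, centred to give 55% or 20% responders; the value less favourable to the device taken in each arm; 1,500 runs per setting.

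| Assumed shape of percent change | Share of missing active subjects scored as successes |
|---|---|
| Normal | 54–61% (Week 3 VAS imputed), 54–62% (absolute change), 63–67% (percent change) |
| Right-skewed | 58–72% across the three variables |
| Bimodal | 60–72% across the three variables |
| Left-skewed (a tail who worsen) | 39–47% (Week 3 VAS), 35–43% (absolute change), 27–42% (percent change) |

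On placebo the range is 0 to 17%. For the Week 3 VAS itself, the active range is roughly 40 to 70%.

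**4. Effect on the criterion.** These counts are illustrations.

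- One active stopper, 17 of the other 31 succeeding, placebo 6 of 32. Scored as failure: (17 − 6)/32 = 34.4 points, missed. Scored as success: (18 − 6)/32 = 37.5 points, met.
- Three active stoppers (32 − 29, the plan's whole dropout allowance in that arm), 16 of the other 29 succeeding, placebo 6 of 32. With none, one, two or three credited: 10/32 = 31.3, 11/32 = 34.4, 12/32 = 37.5 and 13/32 = 40.6 points.
- The uncorrected chi-squared p-values for 16, 17, 18 and 19 active successes against 6 are 0.0085, 0.0042, 0.0019 and 0.0009. Only the 35-point criterion turns on the rule.

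**5. How often one stopper sits on the boundary.** Let X ~ Bin(31, 0.55) be the successes among the other active subjects and Y ~ Bin(32, 0.20) those on placebo. The stopper decides the criterion when X − Y = 11, and P(X − Y = 11) = 0.111. Multiplying by a crediting share of 40 to 70% gives 0.111 × 0.40 = 4.4% to 0.111 × 0.70 = 7.8%. So the rule turns a miss into a success in about 4 to 8% of trials that already contain one active stopper with no rating.

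**The case against.** **The rating may well be given.** A reader might infer that an early stopper can never reach the Week 3 rating. The documents do not support that. Two sections give a calendar anchor, the treatment phase is itself defined as three consecutive weeks, subjects hold the forms at home, and the general adherence sentence can be read as covering assessments. What stands is ambiguity in the timing of the primary endpoint.

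**The rule does not by itself favour the device.** A reader might infer that it scores most active stoppers as successes. That depends on the active arm reaching about 55%, on the shape of the changes and on which variable is imputed. With a left-skewed shape a minority are credited, and that is where the conservative clause has most effect. The contrast between arms remains in every shape examined.

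**The examples sit at the boundary.** This is fair. The one-stopper case was chosen one success short, and the three-stopper case assigns a full arm's dropout allowance to safety stops. The plan expects no adverse events and gives no rate.

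**Stopping criteria.** A reader might infer that the trial has no safety rule for a new wound or infection. The text at hand has none, apart from promising subjects a contact for research-related injury. But the use guide, consent form and case report forms (Appendices D, L and M) and the monitoring plan were not supplied and may contain one.

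**The remedy is itself a convention.** True. A zero change is another single imputation, and own-arm imputation would remain for data missing for other reasons. Recording the rating by calendar answers most of the concern; the scoring rule covers what is left.

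**Conclusion.** The point holds in limited form. The plan is unclear on whether the Week 3 VAS is due after an early stop. If it is missing, the written rule may credit roughly 40 to 70% of active stoppers and roughly 0 to 17% of placebo stoppers (down to 27% of active stoppers if percent change is imputed and changes are left-skewed). Each credited subject adds 3.1 points to a difference judged against a fixed 35.

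This rests on the planned 55% and 20% rates, on assumed distributions, and on at least one such stop with no rating. It can change the result near the threshold; nothing shows that it would usually do so. It merits a low-cost correction and is not a major defect.

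**What to change.** 1. In the 3 Week Evaluation and Evaluation Time Point sections, state that the Week 3 evaluation is recorded at 3 weeks post-baseline whether or not all 42 treatments were given, and that Week 7 follows four weeks later. Counting from baseline matches the labels already used under Secondary Efficacy Outcomes.
2. In Handling of Missing Data, add that an ITT subject in either arm who stopped the device because of an adverse event and has no Week 3 VAS is counted as not meeting the individual success criterion. In the ANCOVA, set that subject's change from Baseline to 0.

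Secondary, and perhaps already covered in Appendices D, L or M: a rule for stopping the device and contacting the site if a foot wound or infection appears, and a question on new foot or health problems on the Day 10, Week 3 and Week 7 forms. If they are covered, a cross-reference is enough.

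**Cost.** A protocol amendment with IRB review. No subjects are added, and the rules are identical for devices A and B, so no unblinding is needed. If the secondary items are adopted, add one question on three forms and a foot examination when a problem is reported. The downside is that the 35-point criterion becomes slightly harder to meet if the active arm has more stops. For example, 16 of 29 (55.2%) with three unrated stoppers becomes 16 of 32 (50.0%). Item 1 limits this, because a stopper who gives a rating is scored on it.
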